## Laboratory Assessments:

Laboratory data that have been obtained using the Site's Local Ranges will be converted to System International (SI) units. The vendor will supply Roche with the Conversion factors to convert the results and local ranges to SI Units. All local units should be incorporated within the Conversion Factors document.

These Conversion Factors will then be reviewed by the Medical Review Team. The conversion factors will be applied directly to the raw data and reported as is; i.e. no adjustment for seemingly incorrect conversions will be performed.

Grading system NCI-CTC version 4 will be used to Grade the relevant tests.

### Hematology and Chemistry Laboratory Data:

Listings will be produced for the hematology and chemistry laboratory parameters (LBCAT=HEMATOLOGY, LBCAT=CHEMISTRY).

Shift tables will also be presented for the laboratory parameters that have NCI CTC grade ranges available from baseline to worst CTC Grade on-treatment, split by High and Low Parameters where applicable.

A Listing of Patients with a CTC Grade 3 at Baseline moving to a CTC Grade 4 will be created, showing the Patient's CTC Grade 4 results.

### Pregnancy:

Pregnancy results will be listed for all women of childbearing potential.

### Serum Hormone:

Serum hormone evaluation tests and results will be listed for all women of childbearing potential.

### Ultrasound:

Ultrasound results will be listed for all women of childbearing potential.

### Creatine Kinase (CPK):

As part of the exploratory analysis, outputs will be produced with Creatine Kinase status (any Abnormal and No Abnormality) versus Treatment Emergent Muscle Spasm status (any Muscle Spasm Adverse Event and No Muscle Spasms).

A Listing of CPK Results and Adverse Events of Muscle Spasms will be created.

A table of CPK Elevations by maximum CTC Grade will be created.

A table of CPK Elevations with the maximum CTC Grade and relative to onset of first Treatment Emergent Muscle Spasm will be created.

A Listing of CPK results and any Adverse Events linked to specific elevated Lab Tests levels which will include CPK, ALT or AST and Renal Insufficiency will be created.

For Patients who consented to Protocol Version 4 and above, a shift table of maximum NCI CTC Grade of CPK Tests, before and after first recorded Treatment Emergent Muscle Spasm will be created.

A graph of CPK Results, together with 95% Confidence Intervals will be created.

## Shift from Baseline to Worst NCI CTCAE Grade During Treatment:

STREAM Template	Description
N/A	
Output ID: t_lb_shift_wrstctc_*
 
 
● Analysis Population: Safety Output will be repeated for each Lab Category.
 
● Column Variables: Baseline CTC Grades 0 to 4
 
● Column Totals: Totals of non-missing Grades, Missing column
 
● Analysis Variables: For each Parameter (in either direction) and Disease Status (Locally Advanced, Metastatic), Worst Post-Baseline CTC Grades 0 to 4, Total of non-missing Grades, Missing row.
 
● Statistics and Calculation Methods: Use proc freq.
 
● Numeric Precision and Formatting of Statistics: Display whole numbers for patient counts and 1 decimal point for percentages.
 

Parameter: Alkaline Phosphatase (High)

Worst NCI-CTC Grade During Treatment Period	Baseline NCI-CTC Grade						Total	Missing
	Grade 0	Grade 1	Grade 2	Grade 3	Grade 4			
Locally Advanced (N=1119)								
Grade 0	787 (70.3%)	29 (2.6%)	1 (<0.1%)	0	0		817 (73.0%)	14 (1.3%)
Grade 1	138 (12.3%)	83 (7.4%)	0	0	0		221 (19.7%)	7 (0.6%)
Grade 2	20 (1.8%)	12 (1.1%)	2 (0.2%)	0	0		34 (3.0%)	0
Grade 3	5 (0.4%)	2 (0.2%)	0	0	0		7 (0.6%)	0
Grade 4	0	0	0	0	0		0	0
Total	950 (84.9%)	126 (11.3%)	3 (0.3%)	0	0		1079 (96.4%)	21 (1.9%)
Missing	0	0	0	0	0		0	0
Metastatic (N=96)								
Grade 0	48 (50.0%)	8 (8.3%)	0	0	0		56 (58.3%)	1 (1.0%)
Grade 1	16 (16.7%)	14 (14.6%)	0	0	0		30 (31.3%)	1 (1.0%)
Grade 2	0	3 (3.1%)	2 (2.1%)	0	0		5 (5.2%)	0
Grade 3	0	0	0	1 (1.0%)	0		1 (1.0%)	0
Grade 4	0	0	0	0	0		0	0
Total	64 (66.7%)	25 (26.0%)	2 (2.1%)	1 (1.0%)	0		92 (95.8%)	2 (2.1%)
Missing	0	0	0	0	0		0	0

Baseline is the patient's last observation prior to initiation of study drug.  
Note: Collected values have been converted using a Sponsor validated conversion file.

### Programming Notes:

- Only include tests which occurred during Treatment.
- Select Worst Post-Baseline Grade for each Parameter and NCI CTC Grade Direction

## Summary of CPK Abnormality Status versus Muscle Spasm Status:

STREAM Template	Description
N/A	
Output ID: t_lb_chi_ck_*
 
 
● Analysis Population: Safety
 
● Column Variables: CK Abnormality, No CK Abnormality
 
● Column Totals: None
 
● Analysis Variables: Muscle Spasm status, p-value (Chi-square).
 
● Statistics and Calculation Methods: Use proc freq with Chi-square test.
 
● Numeric Precision and Formatting of Statistics: Display whole numbers for patient counts and 1 decimal point for percentages.
 
● Optional Subsetting: For Muscle Spasm status, split by Yes and No
 

		CK Abnormality (N=203)	No CK Abnormality (N=279)
Muscle Spasms	Yes	165 ( 81.3%)	206 ( 73.8%)
	No	38 ( 18.7%)	73 ( 26.2%)
p-value (Chi-square)		0.0552	

### Programming Notes:

- A Patient is considered to have a CK Abnormality if they have a CTC Grade 1 or above any time Post-baseline
- A Patient is considered to have a Muscle Spasm if they have a Treatment Emergent Adverse Event of Muscle Spasm.

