5.3.2 Treatment Phase Assessments

Day 1 of the study will be defined as the first day a patient receives vismodegib. One cycle of therapy is defined as 28 days of treatment. During the Treatment Phase, all study assessments will be conducted on Day 1 (± 3 days) of each Cycle, with the exception of tumor evaluation, for which a window of ± 5 days will apply (see below).

The assessments during the treatment period are:

- Limited physical examination at every 28-day visit
- Vital signs (body temperature, blood pressure, and pulse) and weight at every 28-day visit
- ECOG PS assessment at every 28-day visit
- Hematology (including hemoglobin, hematocrit, red blood cell count, full white blood cell count including differential, platelet count, and ANC) at every 28-day visit
- Biochemistry (including glucose, sodium, potassium, chloride, bicarbonate, blood urea nitrogen, creatinine, creatine kinase [also known as creatine phosphokinase], total bilirubin, alkaline phosphatase, AST, and ALT) at every 28-day visit
- Urine pregnancy tests on Day 1 of each subsequent Cycle. If a urine pregnancy test is positive, it must be confirmed by a serum pregnancy test
- 12-lead ECG (during the study if clinically indicated)
- Concomitant therapy and AEs (including SAEs) throughout the study
- For women of childbearing potential:
 - Record date of last menses
 - Ultrasound (as clinically indicated [see Schedule of Assessments])
 - Assess amenorrhea/irregular menses that develops while on study:
 1. At start of amenorrhea/irregular menses, perform serum hormone evaluation at study site, including FSH, LH, E2, and TSH, and refer to gynecologist or appropriate specialist for assessment of ovaries and uterus, including ultrasound
 2. At resolution of amenorrhea/irregular menses, perform serum hormone evaluation at site, including FSH, LH, E2, and TSH. Refer to gynecologist or appropriate specialist for follow-up ultrasound ONLY if there was abnormality identified during previous ultrasound
 3. If amenorrhea/irregular menses recurs, repeat evaluations at start of recurrence as detailed previously
- Vismodegib administration throughout the study
- Tumor assessment (the majority of the patients in this study have locally advanced BCC and in this disease setting measurable tumors are accessible to evaluation by physical examination). Objective responses using RECIST, v1.1 should be confirmed by repeat assessments at least 4 weeks after initial documentation of response:

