5.3.4 Safety Follow-Up Phase Assessments

Patients who discontinue from the study will be asked to return to the clinic for a safety follow-up assessment 1 month, 3 months, 6 months, 9 months, and 12 months after the last dose of vismodegib (+/- 5 days), as provided by this phase II, safety study protocol,

or upon initiation of new non-permitted anti-cancer therapy. The assessments will include:

- Hematology (including hemoglobin, hematocrit, red blood cell count, full white blood cell count including differential, platelet count, and ANC) as clinically indicated
- Biochemistry (including glucose, sodium, potassium, chloride, bicarbonate, BUN, creatinine, creatine kinase [also known as creatine phosphokinase], total bilirubin, alkaline phosphatase, AST, and ALT) as clinically indicated
- Follow up for disease progression
- Concomitant therapy and new anti-cancer therapy
- AEs (including SAEs)
- For women of childbearing potential:
 - Record date of last menses
 - Assess amenorrhea/irregular menses that develops while on study:
 1. At start of amenorrhea/irregular menses, perform serum hormone evaluation at study site, including FSH, LH, E2, and TSH, and refer to gynecologist or appropriate specialist for assessment of ovaries and uterus, including ultrasound
 2. At resolution of amenorrhea/irregular menses, perform serum hormone evaluation at site, including FSH, LH, E2, and TSH. Refer to gynecologist or appropriate specialist for follow-up ultrasound ONLY if there was abnormality identified during previous ultrasound
 3. If amenorrhea/irregular menses recurs, repeat evaluations at start of recurrence as detailed previously
- Patients with metastatic BCC (newly enrolled after approval of the Study Protocol, version 4.0) will complete the M.D. Anderson Symptom Inventory (see Section 5.6 and Appendix 6), prior to having any other assessments performed at the visits
- In selected sites, patients will have blood draws for adverse event–related PK testing if any adverse events that were reported to be related to vismodegib treatment continue to be present at least 6 months after the last dose of vismodegib. Blood samples for the adverse event-related PK testing will be collected at the 6, 9, and 12 months Safety Follow-Up Visits. Blood samples for all time points will be collected even if the adverse event resolves after the 6 months Safety Follow-Up Visit.

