8.2 HYPOTHESIS TESTING

No formal hypothesis testing is planned.

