## Adverse Events:

### General AE Reporting

Listings will include all AEs unless otherwise specified. A Treatment Emergent AE (TEAE) is defined as an AE that starts on or after the first day of study treatment and within 30 days of last dose (please see General Considerations for definition). Unless otherwise specified, AE and SAE summary tables will be restricted to TEAEs.

In STEVIE, the data collection guidelines require that the same AE is entered multiple times into the database, with a separate record for each change in toxicity grade or Lower Level Term. AEs can be reported using this or a “collapsed” Adverse Events analysis dataset.

The Collapsed Adverse Events dataset is derived by combining records that can be reasonably considered to be referring to a single AE term but with changes in toxicity grade (or lower level term). Records from the original AE dataset are grouped, and each group is represented in the collapsed dataset by a single record. The groups are built up by “chaining” records from the original dataset as follows:

- if the Subject ID, System Organ Class and Preferred Term are the same, and
- either the periods defined by the two AEs’ start and end dates overlap, or the Start Date of the later AE is  $\leq 2$  days after the End Date of the earlier one.

In the single record representing the “collapsed” AE:

- Subject ID, System Organ Class and Preferred Term are copied across from any of the records in the group (these are identical so it doesn’t matter which record these variables come from)
- Severity (i.e. toxicity grade) is taken as the most severe grade in the group
- Start Date is taken as the earliest start date in the group
- End Date, Lower Level Term and Outcome are taken from the record with the latest end date in the group

Examples are given on the next page.

Example of derivation of “collapsed” AEs:

Example 1:

SUBJID	System Organ Class	Preferred Term	Lower Level Term	Severity	Outcome	Start Date	End Date
	GASTROINTESTINAL DISORDERS	DYSPEPSI	DYSPEPSIA	GRADE 2 / MODERATE	RESOLVED		
	GASTROINTESTINAL DISORDERS	DYSPEPSI A	HEART BURN	GRADE 3 / SEVERE	RESOLVED		

Collapsed to:

	GASTROINTESTINAL DISORDERS	DYSPEPSI A	HEART BURN	GRADE 3 / SEVERE	RESOLVED		
--	----------------------------	------------	------------	------------------	----------	--	--

Example 2:

SUBJID	System Organ Class	Preferred Term	Lower Level Term	Severity	Outcome	Start Date	End Date

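### The chi-square p-value for CK abnormality against muscle spasm is no evidence on a link: both ever/never indicators depend on time on treatment, and their windows differ

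*SAP*

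**What the plan says.** The SAP section Summary of CPK Abnormality Status versus Muscle Spasm Status gives the method as "Use proc freq with Chi-square test" and lists the p-value among the displayed rows. Its programming notes define the two variables:

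- CK: "A Patient is considered to have a CK Abnormality if they have a CTC Grade 1 or above any time Post-baseline". No end date is set.
- Spasm: "A Patient is considered to have a Muscle Spasm if they have a Treatment Emergent Adverse Event of Muscle Spasm". The SAP's General AE Reporting section defines a treatment-emergent event as "an AE that starts on or after the first day of study treatment and within 30 days of last dose".

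The schedule of CK tests comes from the protocol. In section 5.3.2 the on-treatment chemistry panel includes "creatine kinase [also known as creatine phosphokinase], total bilirubin, alkaline phosphatase, AST, and ALT) at every 28-day visit". In section 5.3.4, after treatment, the same panel is done only as needed: "creatine kinase [also known as creatine phosphokinase], total bilirubin, alkaline phosphatase, AST, and ALT) as clinically indicated".

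The SAP section Creatine Kinase (CPK) labels these outputs exploratory. Protocol section 8.2 states "No formal hypothesis testing is planned". None of the SAP's CK outputs adjusts for treatment duration or for the number of CK tests.

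**The concern.** A patient treated for longer has more scheduled CK tests and more time in which a spasm can be counted. The two indicators therefore share a cause, time on treatment, and can be associated across patients without being associated at any given exposure. The windows also differ: a CK result from a late follow-up visit counts, while a spasm arising at that time does not. A two-by-two table of ever/never indicators also hides which came first.

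What is at stake is interpretation. Safety is the primary objective, CK is a natural candidate marker of muscle toxicity, and this is the only p-value found in the SAP text available. At 0.055 it invites reading either as near-evidence of a link or as evidence of none.

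**Working it through.** **Reproducing the displayed figure.** The SAP display has spasm in 165 of 203 CK-abnormal patients (81.3%) and in 206 of 279 others (73.8%).

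- Cross-product: 165 × 73 - 38 × 206 = 12,045 - 7,828 = 4,217.
- Uncorrected Pearson chi-square: 482 × 4,217² / (203 × 279 × 371 × 111) = 3.675 on 1 df, p = 0.0552. This matches the display.
- Difference 7.4 points; odds ratio 12,045 / 7,828 = 1.54 (95% CI 0.99 to 2.39).

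**Why exposure matters.** Let T be time on treatment, and let p_S(T) and p_C(T) be the chances of being counted as spasm and as CK-abnormal. If the two are independent given T, then across patients

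Cov(S, C) = Cov(p_S(T), p_C(T)), and the false risk difference is Cov(S, C) / [P(C)(1 - P(C))].

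This is zero only if the two probabilities are uncorrelated over T. It is positive if both rise with T. It is negative if patients with a spasm tend to stop early, so that short T goes with spasm. In the display, P(C) = 203/482 = 0.421 and P(C)(1 - P(C)) = 0.244. The covariance is 4,217 / 482² = 0.018, and 0.018 / 0.244 gives the 7.4 points. A covariance of that size between two exposure-driven probabilities would be enough to produce the table.

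**How large it could be.** The documents do not give exposure by table cell, spasm onset times or the start of CK testing. The scenarios below are therefore assumptions. All have n = 482, about 42% CK-abnormal, and no CK-spasm link given exposure.

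Scenarios A and B take exponential exposure capped at 36 months and 77.0% with spasm (371/482). The median of 9.7 months is borrowed from the locally advanced cohort of the earlier phase II trial described in protocol section 1.1.2.2.

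- A. CK observed throughout treatment. Constant spasm hazard: 92.0% against 66.0%, +26.0 points, 100% rejection at nominal 5%. 90% of patients susceptible: 87.0% against 69.7%, +17.3 points, over 99%. 80% susceptible with early onset: 79.8% against 74.9%, +4.9 points, 24%.
- B. As A, with CK observed for 12 further months in everyone: +12.0, +7.8 and +2.1 points; rejection 88%, 52% and 8%.

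Scenarios C and D take gamma exposure with mean 12 months (before any early stopping) and shape 1, 2 or 4, with early spasm onset (mean 2 months, 80% susceptible).

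- C. CK testing starts at a uniformly distributed time over months 0 to 18: +1.7, +1.0 and +0.3 points; rejection 3% to 8%.
- D. 60% of spasm patients stop treatment a mean of 3 months after the spasm: -2.0, -7.8 and -9.9 points.

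Early stopping does not always reverse the sign. In the 90%-susceptible version of A, with 25% to 75% of spasm patients stopping a mean of 3 months later, the odds ratio was still 2.29 to 1.36.

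**Effect of stratifying.** In the six settings of A and B, a Cochran-Mantel-Haenszel test stratified by exposure decile rejected 4.8% to 5.3% of the time, against 8% to 100% for the crude test. The adjusted result for this trial cannot be computed from the documents.

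**What the SAP displays show about the windows.** CK status is available for 482 patients, against 1215 in the safety population (Summary of Deaths). In the version 4 and later subset, 514 of 677 patients have a CPK value at any time after consent to that version, but only 432 have one on treatment or within 30 days. So 514 - 432 = 82 (16%) appear to have values only outside the window in which a spasm can count. The table of CK timing relative to first spasm has 62 spasm patients with a CPK value, counting first spasms after version 4 consent, against 371 spasm patients here. The populations may differ, but this suggests that many spasms came before CK testing began.

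**The case against.** The strongest case for leaving the table alone has four parts.

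First, the analysis is exploratory and no objective, stopping rule or decision depends on it. That stands and keeps the point minor. Nor does an exploratory p-value strictly contradict the protocol's statement on formal testing; removing it is simply in keeping with that statement.

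Second, order is described elsewhere. The timing table shows CK elevation in 12 of 43 spasm patients (27.9%) before the first spasm and in 25 of 60 (41.7%) after it, and there is a before/after shift table and a listing. That stands in part. Those outputs cover a subset, are not adjusted for exposure and do not alter the chi-square.

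Third, the bias may be negligible. Scenario C shows this if spasms come early and CK testing starts late, and the CK counts above make a late start plausible. That stands as a limit on any claim about size.

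Fourth, its sign is open. Adverse events are a recorded reason for stopping treatment, and scenario D gives negative differences. That also stands.

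A reader might therefore infer too much: that longer treatment by itself explains the association, that the bias must be upward, or that the p-value mainly reflects the spread in exposure. The documents support none of these. That 7.4 points falls inside the simulated range does not show that exposure produced it.

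**Conclusion.** The concern holds in a limited form. An unadjusted chi-square is applied to two ever/never indicators that both depend on treatment duration and are observed over different windows. With no CK-spasm link given exposure, the test need not keep its 5% level. Across the assumed scenarios the false difference runs from about -10 to +26 points, with rejection from 3% to 100%.

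Where this trial falls depends on spasm onset, on when CK testing began and on whether spasm shortened treatment. The documents give none of these. The calculation of 0.0552 is correct, but the figure is not evidence for or against a CK-spasm link. Severity is low.

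**What to change.** Delete the chi-square test and its p-value row from t_lb_chi_ck_* and keep the counts and percentages as description. This removes one row and needs no new data.

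If a measure of association is wanted, restrict both variables to the same on-treatment window, from the first post-baseline CK test to 30 days after last dose. Report a Cochran-Mantel-Haenszel odds ratio with 95% CI, stratified by exposure. State how patients whose first spasm preceded the first CK test are handled. This deals with exposure and window but not with order, and it costs a smaller analysis set and a less precise estimate.

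A Cox model for time to first spasm with CK as a time-dependent covariate would address order and is optional. The SAP should then say that it excludes patients whose first spasm came before CK testing, and that it may rest on few events: the timing table has 62 spasm patients with a CPK value, 43 with a value before the spasm and 12 with a prior elevation.

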## Summary of CPK Elevations, by Maximum CTC Grade:

STREAM Template	Description
N/A	
Output ID: t_lb_ck_*
 
 
● Analysis Population: Safety and consented to Protocol Version 4 and above
 
● Column Variables: Any time post-PV4+, On-treatment only (including 30 days after treatment discontinuation)
 
● Column Totals: None
 
● Analysis Variables: Patients with at least 1 CPK result, No Elevated CPK result, Any Elevated CPK Result.
 
● Statistics and Calculation Methods: Use proc freq.
 
● Numeric Precision and Formatting of Statistics: Display whole numbers for patient counts and 1 decimal point for percentages.
 
● Optional Subsetting: For Any Elevated CPK result, split by Max CPK Grade 1-2 and Max CPK Grade 3-4
 

	Any time post-PV4+			On-treatment only (incl. 30 days after treatment discontinuation)		
	n	% of all patients (N=677)	% of patients with >=1 CPK value	n	% of all patients (N=677)	% of patients with >=1 CPK value
Patients with >=1 CPK value	514	75.9%	100.0%	432	63.8%	100.0%
No elevated CPK (all measurements normal)	310	45.8%	60.3%	243	35.9%	56.3%
Any elevated CPK	204	30.1%	39.7%	169	27.9%	43.8%
Max CPK grade 1-2	193	28.5%	37.5%	178	26.3%	41.2%
Max CPK grade 3-4	11	1.6%	2.1%	11	1.6%	2.5%

### Programming Notes:

- Only include Patients that have consented to Protocol Version 4 and above
- Select Worst Post-Baseline Grade for CPK tests within each Patient and group by Grades 1-2 and 3-4

Summary of CPK Elevations and Muscle Spasm AEs including Relative Timing of CPK Elevations with onset of First Muscle Spasm:

STREAM Template	Description
N/A	
Output ID: t_ck_ms_*
 
 
● Analysis Population: Safety and consented to Protocol Version 4 and above
 
● Column Variables: No Muscle Spasm, With Muscle Spasm at any time, Prior to onset of 1st Muscle Spasm, After onset of 1st Muscle Spasm
 
● Column Totals: None
 
● Analysis Variables: Patients with at least 1 CPK result, No Elevated CPK result, Any Elevated CPK Result.
 
● Statistics and Calculation Methods: Use proc freq.
 
● Numeric Precision and Formatting of Statistics: Display whole numbers for patient counts and 1 decimal point for percentages.
 
● Optional Subsetting: For Any Elevated CPK result, split by Max CPK Grade 1, 2, 3 and 4
 

	With muscle spasm			
	No muscle spasm	At any time	Prior to onset of 1st muscle spasm	After onset of 1st muscle spasm
Patients with >=1 CPK value	120	62	43	60
No CPK elevation	76 ( 63.3%)	35 ( 56.5%)	31 ( 72.1%)	35 ( 58.3%)
Any CPK elevation	44 ( 36.7%)	27 ( 43.5%)	12 ( 27.9%)	25 ( 41.7%)
Max grade 1	36 ( 30.0%)	19 ( 30.6%)	10 ( 23.3%)	18 ( 30.0%)
Max grade 2	4 ( 3.3%)	5 ( 8.1%)	1 ( 2.3%)	5 ( 8.3%)
Max grade 3	3 ( 2.5%)	2 ( 3.2%)	1 ( 2.3%)	1 ( 1.7%)
Max grade 4	1 ( 0.8%)	1 ( 1.6%)	0	1 ( 1.7%)

Programming Notes:

- Only include Patients that have consented to Protocol Version 4 and above
- Select Worst Post-Baseline Grade for CPK tests within each Patient
- First Muscle Spasm refers to the first occurrence of Muscle Spasm after Protocol Version 4 consent date

Shift Table of Maximum CPK CTC Grade before and after onset of First Muscle Spasm:

STREAM Template	Description
N/A	
Output ID: t_ck_ms_shift_*
 
 
● Analysis Population: Safety and consented to Protocol Version 4 and above
 
● Column Variables: Max CTC grade after onset of 1st Muscle Spasm
 
● Column Totals: None but include Missing column
 
● Analysis Variables: Max CTC Grade prior to onset of 1st Muscle Spasm, include Missing row
 
● Statistics and Calculation Methods: Use proc freq.
 
● Numeric Precision and Formatting of Statistics: Display whole numbers for patient counts and 1 decimal point for percentages.
 
● Optional Subsetting: For Max CTC Grade, split by Max CPK Grade 0, 1, 2, 3 and 4
 

Max. CPK grade after onset of 1st muscle spasm						
Max. CPK grade prior to onset of 1st muscle spasm	0	1	2	3	4	Missing
0	23	4	0	1	1	2
1	1	7	2	0	0	0
2	1	0	0	0	0	0
3	0	0	1	0	0	0
4	0	0	0	0	0	0
Missing	10	7	2	0	0	1

[figure not shown]
Programming Notes:

- Only include Patients that have consented to Protocol Version 4 and above
- Select Worst Post-Baseline Grade for CPK tests within each Patient
- First Muscle Spasm refers to the first occurrence of Muscle Spasm after Protocol Version 4 consent date

Plot of Mean and 95% CI of CPK over Time:

STREAM Template	Description
MNG01	
Output ID: g_lb_ck_*
 
 
● Analysis Population: Safety
 
● Plot: 1 Line per Disease Status (Locally Advanced and Metastatic)
 
● Y Axis: CPK Result
 
● X Axis: Analysis Visits (use tick-marks for each Visit)
 
● Methods: Use Standard STREAM method.
 
● Numeric Precision and Formatting of Statistics: Display whole numbers for Y Axis and Visit descriptions for X Axis.
 
● Optional Additions: Include N counts underneath each Visit for each Disease Status. Include Safety Population N count for each Disease Status in Legend.
 

Programming Notes:

- Include all visits from Baseline

Listing of CPK Results and Adverse Events of Muscle Spasm:

STREAM Template	Description
N/A	Output ID: I_ck_ae_* 
 
● Analysis Population: Safety
 
● Column Variables: For Lab Data include Visit, Sample Date(with study Day), CPK Standard Result and CTC Grade. For Adverse Events of Muscle Spasm, include Reported Term, Start and End Date and CTC Grade
 

